Title: *ABCA3* gene and RDS in late preterm and term infants

NCT number: NCT04137783

Date of document: March 16, 2021

Neonatal respiratory distress syndrome (RDS) is caused by the deficiency or inactivation of pulmonary surfactant, and is commonly seen in early preterm infants due to their immature lung development. However, some maternal and neonatal characteristics in late preterm and term infants such as maternal diabetes, meconium aspirated pneumonia, neonatal sepsis, and severe intrapartum asphyxia, could also contribute to RDS. Existing evidence has demonstrated that RDS in late preterm and term infants is a somewhat distinct disease entity, with risk factors and clinical profiles that differ from those in early preterm infants ^[1-3]. In a neonatal unit, some late preterm or term infants experience RDS; however, the etiology has not been well defined after a routine workup. This unique RDS entity was referred to as unexplained respiratory distress syndrome (URDS) by numerous previous studies, as well as our study ^[4-7].

Given that a large body of literature has demonstrated the essential role genetic mechanism play in the pathogenesis of most URDS cases, numerous medical facilities have carried out clinical exome sequencing to identify the underlying genetic cause of URDS ^[8-10]. Among all of the genetic factors that contribute to the RDS, the most common is *ABCA3* gene mutation, which involves the assembly of pulmonary surfactant in the lamellar body of pneumocyte II ^[11]. Existing evidence indicated that patients with homozygous or compound heterozygous *ABCA3* gene mutations were commonly in critically ill conditions ^[12]. A single *ABCA3* mutation was also likely to increase the risk and severity of RDS ^[4, 13].

Unfortunately, in a considerable proportion of neonatal URDS patients, genetic testing fails to yield any abnormal findings, making these patients the “true URDS” patients. Currently, whether the *ABCA3*-mutated URDS patients have similar or more challenging clinical profiles to those without any genetic abnormalities continues to confound most neonatologists. An answer to this question would help to guide the management and predict

the clinical outcomes of neonatal URDS patients. The present study aimed to address this by comparing the clinical characteristics of late preterm and term infants with severe URDS with homozygous or compound heterozygous *ABCA3* mutations, a single *ABCA3* mutation, or no defined genetic abnormalities.

Patient selection

This single-center retrospective cohort study involved infants ≥ 34 weeks' gestation with severe URDS who were admitted to Children's Hospital of Chongqing Medical University between January 2013 and December 2019. In this study, severe RDS was mainly defined according to the consensus of the Pediatric Acute Lung Injury Consensus Conference ^[14], and Montreux definition ^[15]: (1) manifestations and chest radiograph compatible with RDS; (2) on invasive mechanical ventilation with oxygenation index ≥ 16 , which was calculated based on the daily blood gas, or as an alternative measurement, on the subcutaneous oxygen tension ^[16, 17].

Almost all infants with severe RDS had undergone a comprehensive workup, including serial infection markers, chest radiograph, echocardiography, and blood and sputum pathogen testing. For all patients with severe RDS who responded inadequately to interventions and had unremarkable workup findings, trio exome sequencing on samples from patients and their parents were usually recommended. All URDS patients who underwent genetic testing were enrolled in this study. Those whose parents rejected genetic testing, or who had cardiopulmonary malformations, pulmonary hypoplasia, culture-positive sepsis, or known respiratory disease-associated gene mutations (such as *SFTPA1*, *SFTPA2*, *SFTPB*, *SFTPC*, *CHPT1*, *LPCAT1*, *PCYT1B*, *NKX2*, *CFTR*, and *FOXF1*)

were excluded. This study was approved by the Institutional Review Board of Children's Hospital of the Chongqing Medical University (No.2018-158) and was registered on clinicaltrials.gov (NCT04137783).

Exome sequencing and gene mutation detection

All infants in this study underwent trio exome sequencing after written consent had been obtained from their parents. A gene company (Chigene, Beijing) offered the sequencing as a clinical laboratory service. Sequence analysis of coding exons and flanking introns were performed as previously described^[18,19]. All samples were analyzed to detect frame-shift mutations, nonsense mutations, missense mutations, splicing site mutations, and in-frame indel mutations. Assessment of copy number variation was also performed from exome sequencing data using computational tools. A variant was strictly defined as a mutation if it had been previously described to cause disease with a presentation consistent with these patients, or resulted in an amino acid change or protein structure alteration to disrupt protein function that was predicted by both SIFT and PolyPhen for missense mutations^[20,21], and MaxEntScan and dbSNV for splicing site mutations^[22]. In the case of a novel mutation, phastCons and phyloP were used to determine the evolutionary conservation of the region where the mutation was located^[23]. The American College of Medical Genetics and Genomics/Association for Molecular Pathology (ACMG-AMP) criteria were applied to interpret the mutations^[24]. The subjects in this study were categorized into three groups: homozygous or compound heterozygous *ABCA3* mutations, a single *ABCA3* mutation, and no defined genetic abnormalities.

Clinical profiles data

All relevant clinical data were extracted from a hospital information system.

All antepartum and postpartum data were collected and included: maternal age, parity, and pregnancy-related complications; mode of birth, amniotic fluid condition, and history of asphyxia and resuscitation; postnatal age of respiratory symptom onset, modalities of respiratory support, and the daily record of blood gas and subcutaneous oxygen tension; laboratory data including complete blood count, C-reactive protein, procalcitonin, blood and sputum culture, respiratory viral detection test, and genetic testing; radiographic examination including chest X-ray and echocardiogram; medications taken during the hospital stay.

Radiological scoring

All chest X-rays were reviewed on a hospital information system by one radiologist. The most severe images were scored according to the Fleischner Society criteria^[25]. The chest X-ray was rated in three sections on both sides of the lung: apex to the carina, carina to the lower pulmonary vein, and lower pulmonary vein to the diaphragm. The incidence of radiological features, including ground-glass opacity, reticular pattern, air bronchogram, atelectasis, and air leak, were evaluated for each lung section. Each finding was scored as 0 = none, 1 = discrete, 2 = diffuse, or 3 = strong at each section. An overall cumulative score was calculated by adding the individual section scores together, with a maximum score of 18 for each patient.

Statistical Analysis

Analysis of variance (ANOVA) and the Chi-square or Fisher's exact tests were used to compare clinical characteristics and radiographic scores between different groups of patients. Tests for the differences in the age of symptom onset and the age of development of severe RDS between the groups were carried out using the log-rank test. A two-tailed *p*-value of

<0.05 was considered statistically significant.

References

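### Only the comparator group has to be free of other genetic abnormalities; one rule on non-ABCA3 findings should apply to all three groups

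*Combined protocol and SAP*

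**What the plan says.** The combined protocol and SAP touches on this in three places.

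- **Introduction (untitled).** The comparator is described as patients in whom "genetic testing fails to yield any abnormal findings". The question is whether ABCA3-mutated infants have "similar or more challenging clinical profiles to those without any genetic abnormalities".
- **Patient selection.** Enrolment is broad: "All URDS patients who underwent genetic testing were enrolled in this study". The one genetic exclusion, applied to the whole cohort, is for "known respiratory disease-associated gene mutations", followed by a list of examples. Disorders outside the respiratory field are not mentioned.
- **Exome sequencing and gene mutation detection.** The grouping rule reads: "The subjects in this study were categorized into three groups: homozygous or compound heterozygous *ABCA3* mutations, a single *ABCA3* mutation, and no defined genetic abnormalities". Testing is exome-wide and not limited to a surfactant-gene panel: "Assessment of copy number variation was also performed from exome sequencing data using computational tools". A variant counts as a mutation by either of two routes. It is already known to cause disease that fits these patients' presentation, or it is predicted to disrupt the protein. Only the first route is tied to the phenotype.

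The Statistical Analysis section lists ANOVA, chi-square or Fisher tests and log-rank tests, all unadjusted. No section says how an infant with a non-respiratory genetic diagnosis is grouped or counted.

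**The concern.** The study asks what an ABCA3 mutation adds to the clinical picture. That needs groups which differ in ABCA3 status and are otherwise formed by the same rule. Here the condition of having no other genetic abnormality is written for the comparator only. A second disorder can therefore contribute to outcomes in the ABCA3 groups, while the same disorder is removed from the reference group. Any effect it has on an outcome would be attributed to ABCA3. This matters most for the single-mutation group, where the contribution of ABCA3 is least settled.

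There is also a practical problem. Two analysts working from the same exome reports could form different comparators, depending on how each reads *defined*.

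**Working it through.** **Step 1: apply the grouping text to each kind of enrolled infant.** Infants with another respiratory gene mutation have already been excluded everywhere.

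| Infant | Broad reading of *defined* (any finding) | Narrow reading (fits the presentation) |
|---|---|---|
| ABCA3 mutation(s) only | ABCA3 group | ABCA3 group |
| ABCA3 mutation(s) plus non-respiratory diagnosis | ABCA3 group | ABCA3 group |
| Non-respiratory diagnosis only | no group | comparator |
| Neither | comparator | comparator |

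Under the broad reading the groups are not exhaustive and the extra condition falls on one side only. Under the narrow reading all enrolled infants are placed and the asymmetry largely disappears. The introduction's wording, the exome-wide and copy-number scope, and the second route of the mutation definition favour the broad reading. The first route allows the narrow one.

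**Step 2: look for a figure to reproduce.** There is none. The documents give no group sizes, power, effect size or frequency of second findings. The only numeric input to the tests is the two-sided 0.05 level. Everything below is illustration on assumed values.

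**Step 3: size of the shift under the broad reading.** Suppose ABCA3 has no effect. Let q be the share of an ABCA3 group with a second disorder, and d the effect of that disorder on the outcome in SD units. The comparator share is 0 by definition, so

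shift = q × d.

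- q from 2% to 20%, d from +0.5 to +1.0: 0.02 × 0.5 = +0.01 SD up to 0.20 × 1.0 = +0.20 SD, towards ABCA3 being worse.
- The same q, d = −0.5: −0.01 to −0.10 SD, the opposite way.
- d = 0: no shift.
- q = 10%, d = 1: 0.10 SD.

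For a binary outcome, the shift is q × (risk with the second disorder − base risk). With q = 10% and a base risk of 30%:

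- 0.10 × (60% − 30%) = +3.0 points.
- 0.10 × (15% − 30%) = −1.5 points.

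**Step 4: effect on the false-positive rate.** This uses a normal approximation for two groups of n infants, with standard error √(2/n):

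rejection rate = Φ(shift/SE − 1.96) + Φ(−shift/SE − 1.96).

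A shift of 0 returns 5%, as it should. For a shift of 0.10 SD and n = 30, SE = √(2/30) = 0.258 and shift/SE = 0.387, which gives 6.7%. With n = 10 it is 5.6%, and with n = 100 it is 10.9%. At the extreme corner of 0.20 SD the rates are 7.3%, 12.1% and 29.3% for n = 10, 30 and 100.

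**Step 5: after the change.**

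- *Exclude from all groups:* the share is 0 everywhere, so the shift from this source is 0 whatever the sign of d.
- *Keep in all groups:* the residual is (q_A − q_C) × d, where q_A and q_C are the shares in the ABCA3 and comparator groups. It is 0 if the shares are equal. With shares of 5% against 10%, either way round, and d from −0.5 to 1.0, it lies between −0.05 and +0.05 SD.

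**The case against.** The best case against the point has four parts.

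First, the operative word is *defined*, and the same section ties one route of its mutation definition to the patients' presentation. On that reading an unrelated disorder is not a mutation and the infant stays in the comparator. The plan also says that the subjects were placed in three groups, which suggests that nobody was left over. This stands as a possible reading. But the second route carries no such restriction, and the plan never says that the narrow reading applies.

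Second, few infants may be affected. Cardiopulmonary malformations and pulmonary hypoplasia are excluded, and sequencing was usually recommended after an unremarkable workup. The gene exclusion is open-ended ("known respiratory disease-associated gene mutations (such as" introduces examples only), so a neuromuscular or metabolic gene that drives respiratory failure might be treated as already excluded. This stands, and it is why the effect is probably small.

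Third, a reader might infer that the bias runs in one direction and favours ABCA3 being worse. The documents do not support that. It follows only if the second disorder worsens the outcome compared. Every infant had to reach an oxygenation index of at least 16 on invasive ventilation, and one with another disorder might get there with less intrinsic lung disease. The sign could then reverse for the radiographic score, age at symptom onset and age at severe RDS, which are the outcomes that the analysis section names specifically.

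Fourth, a reader might infer that affected infants were in fact dropped, or that the shift is large. The documents report no such infant and no frequency, so neither can be claimed.

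**Conclusion.** The point holds as a cheap improvement. As written, the condition on other genetic abnormalities applies to the comparator only, the cohort-wide exclusion does not close the gap, and the unadjusted tests do not correct for it. The contrast may therefore be biased, in a direction that depends on how a second disorder affects each outcome.

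The size cannot be computed from the documents. On assumed shares of 2% to 20% and effects of −0.5 to +1.0 SD, it runs from −0.10 to +0.20 SD. The central illustration (10% and 1 SD) is 0.10 SD, with a false-positive rate of 6.7% at an assumed 30 infants per group. The conclusion rests on the broad reading of *defined*, which the text favours without settling. The recommendation does not depend on that reading or on the direction of the bias, because one common rule removes the asymmetry either way.

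**What to change.** 1. Apply one rule to all three groups: exclude any infant with another pathogenic or likely pathogenic finding, sequence or copy-number, whatever the ABCA3 status. The plan already applies the ACMG-AMP criteria, so no new classification system is needed.
2. Restate the groups as: two ABCA3 mutations and no other genetic diagnosis; one ABCA3 mutation and no other genetic diagnosis; no genetic diagnosis.
3. Report the number of infants removed under this rule, by ABCA3 status.
4. Add a sensitivity analysis that keeps these infants in all groups, with the ABCA3-negative ones in the comparator. Note beside it that it removes the bias only if the shares with a second disorder are similar across groups.

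The cost is a few sentences in the Patient selection and exome sequencing sections and a re-read of exome reports already held. The downside is possibly a few infants fewer in the ABCA3 groups.

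### The plan has no step masking the single radiologist to genotype, although the subjective chest X-ray score is compared between genotype groups

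*Combined protocol and SAP*

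**What the plan says.** The plan is a short combined protocol and analysis text for a retrospective, single-center cohort.

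- **Reader.** Radiological scoring: "All chest X-rays were reviewed on a hospital information system by one radiologist".
- **Image scored.** Same section: "The most severe images were scored according to the Fleischner Society criteria". The sentence is passive. It gives no rule or time window for choosing the image and does not say who chose it.
- **Scale.** "Each finding was scored as 0 = none, 1 = discrete, 2 = diffuse, or 3 = strong at each section", and then "An overall cumulative score was calculated by adding the individual section scores together, with a maximum score of 18 for each patient".
- **Groups.** Exome sequencing and gene mutation detection: "The subjects in this study were categorized into three groups". The groups are two mutated *ABCA3* copies, one mutated copy, and no genetic finding.
- **Comparison.** Statistical Analysis uses ANOVA and chi-square or Fisher's exact tests to "compare clinical characteristics and radiographic scores between different groups of patients", at a two-tailed 5% level.
- **Data source.** Clinical profiles data: "All relevant clinical data were extracted from a hospital information system". The laboratory items listed there end with "respiratory viral detection test, and genetic testing".

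The document mentions no masking to genotype, no removal of identifiers from films and no random reading order.

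**The concern.** The score depends on judgement: the four grades are words with no stated thresholds between them. Choosing the most severe image is a second judgement. The score is then compared across the very groups whose identity could color those judgements.

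The plan itself suggests a direction. Its introduction reports that infants with two mutated copies tend to be critically ill, and it asks whether infants with *ABCA3* mutations fare similarly to or worse than infants without a genetic finding. A reader who knew both the question and the genotype would have a reason, without intending it, to grade one group higher.

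Because the study is retrospective, genotype may have been known by the time the films were read. At stake is whether a difference in the radiographic score can be read as a difference in lung disease.

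**Working it through.** **Step 1. Is masking stated anywhere?** The concern rests on an omission, so the check is to set the sections side by side.

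| Section | What it gives | Masking to genotype |
|---|---|---|
| Patient selection | Retrospective cohort, 2013 to 2019 | Not mentioned |
| Exome sequencing and gene mutation detection | Three genotype groups; sequencing by an outside company | Not mentioned |
| Clinical profiles data | Hospital information system as source; genetic testing listed | Not mentioned |
| Radiological scoring | One reader, worst images, grades 0 to 3, summed | Not mentioned |
| Statistical Analysis | Scores compared between groups | Not mentioned |

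The Radiological scoring section reads as complete prose, with no sign of removed text.

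**Step 2. The plan's own figure.** The only figure given for the score is its maximum, 18. Three sections on two sides with a top grade of 3 give 3 × 2 × 3 = 18, so it reproduces with one grade per section. Grading all five listed findings in each section would give 5 × 6 × 3 = 90. That is a separate question about the scale. The illustration below is in SD units and does not depend on the answer.

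**Step 3. What a reading shift would do.** The plan gives no group sizes, no SD and no estimate of reader bias, so every input here except the 5% level is an assumption. The summed score is taken to be analyzed by one-way ANOVA.

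Suppose there is no true difference and one group is read higher by *d* SD. With group sizes nᵢ, shifts sᵢ (equal to *d* in that group and 0 elsewhere) and weighted mean shift s̄, the noncentrality is

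λ = Σ nᵢ (sᵢ − s̄)²

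and the false-positive rate is P[F(2, N − 3; λ) > F₀.₉₅(2, N − 3)].

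For 20/20/20 infants and *d* = 0.25:

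- s̄ = 0.25/3 = 0.0833
- λ = 20 × [(0.1667)² + 2 × (0.0833)²] = 20 × 0.04167 = 0.833
- critical value F₀.₉₅(2, 57) = 3.159
- rejection rate = 11.4%, against 5% with no shift

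Other assumptions give:

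| Assumed group sizes | Group shifted | *d* = 0.25 | *d* = 0.5 |
|---|---|---|---|
| 10/10/10 | any one | 7.9% | 17.8% |
| 20/20/20 | any one | 11.4% | 33.7% |
| 10/10/30 | a group of 10 | 8.7% | 21.4% |

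With unequal groups, the result also depends on which group is shifted. At 10/10/30 and *d* = 0.33, the rate is 11.8% if a group of 10 is shifted and 15.5% if the group of 30 is.

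These figures show how the test would respond to a shift. They are not evidence that a shift occurred.

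**The case against.** The strongest reply is that silence is not evidence of an unmasked reading. This is a brief methods text with one paragraph on imaging, and masking may have been done and not reported. **This stands**, and it is why the point is conditional.

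Four stronger readings are tempting, and the document supports none of them:

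- **That the radiologist knew the genotype.** Films were reviewed on a hospital information system, and genetic testing is among the data extracted from one. That does not show what the reader had open, or whether the reading came before or after the genetic result. An outside company did the sequencing.
- **That the radiologist chose the worst film by eye.** This is a natural reading of adjoining sentences, but the text does not say who chose the image or how.
- **That masking to outcome is also needed.** The planned comparison is between genotype groups, and nothing in the plan relates the score to an outcome. Genotype is the relevant item.
- **That the calculated rates measure bias in this study.** Shift, SD and group sizes are all assumed, and the results vary widely with them.

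It is also fair to say that the reach is limited. No primary endpoint is named, the score is one of several characteristics compared, and the log-rank tests on age at symptom onset and age at severe RDS do not use it. That limits the importance of the point but does not answer it: as written, nothing protects the radiographic comparison from reader expectation.

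**Conclusion.** The point holds in a limited form, as a cheap improvement. The plan compares a subjective, single-reader score between genotype groups and includes no masking of the reader to genotype. If the reading was unmasked, the radiographic comparison could partly reflect expectation, in a direction that the introduction suggests.

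The effect cannot be sized from the document. The 11.4% figure is one labelled illustration, resting on an assumed 20 infants per group, an assumed 0.25 SD shift in one group, and no true difference. The conclusion does not extend to the other comparisons, and it is not a finding that the reading was biased.

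**What to change.** Make genotype masking part of the reading procedure: export the films without identifiers and in random order, and have the same radiologist select and score them without knowing the genotype.

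- **If the films were already read masked to genotype,** say so, covering both selection and scoring. One sentence is enough.
- **If they were read unmasked,** repeat the reading in this way after a washout interval and use the masked scores in the ANOVA.

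The cost is the radiologist's time and the work of exporting the films. No extra reader and no new imaging are needed. The main downside is that the same reader may still recall some films despite the washout; random order and removal of identifiers reduce this but may not remove it. A second masked reader would avoid the recall problem and allow an agreement check, at the cost of another reader. That is an option, not a requirement.

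### The analysis plan gives only group tests at p<0.05, with no effect estimates, intervals or follow-up contrasts, so it cannot support an answer of similar or attribute a difference to one ABCA3 group

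*Combined protocol and SAP*

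**What the plan says.** The unheaded background poses the question: whether infants with ABCA3 mutations "have similar or more challenging clinical profiles to those without any genetic abnormalities". It adds a practical purpose: "An answer to this question would help to guide the management and predict" (clinical outcomes, as the sentence goes on to say). It also gives a separate expectation for each mutation class. Infants with two mutated alleles "were commonly in critically ill conditions", while a single "mutation was also likely to increase the risk and severity of RDS".

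The aim then ties the analysis to that question: "The present study aimed to address this by comparing the clinical characteristics of late preterm and term infants with severe URDS" in three groups, namely homozygous or compound heterozygous ABCA3 mutations (biallelic below), a single ABCA3 mutation, and no defined genetic abnormality. The section on exome sequencing and gene mutation detection repeats this grouping.

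The Statistical Analysis section has three sentences. ANOVA and chi-square or Fisher's exact tests "were used to compare clinical characteristics and radiographic scores between different groups of patients". Log-rank tests compare age at symptom onset and age at development of severe RDS. Significance is two-tailed p<0.05. Neither that section nor any other mentions a mean or risk difference, a hazard ratio, a confidence interval, a margin for similarity, or a comparison to follow a three-group test.

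**The concern.** The question has two possible answers, similar or more severe, and the planned methods serve neither well.

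- **More severe.** A three-group test asks whether all three groups share one distribution. If it rejects, the reader does not learn whether the biallelic group, the single-mutation group or both differ from the infants without an abnormality. The background treats that distinction as clinically relevant.
- **Similar.** A test of no difference that fails to reject fits true similarity and also fits too few infants to tell. Without an interval the two cannot be separated.

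The answer is meant to inform management and prognosis. A bare non-significant p-value for the single-mutation group, for example, could be taken as reassurance that the data do not provide.

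**Working it through.** **Inputs from the document.** Three groups; three outcomes named individually in the Statistical Analysis section (radiographic score, age at symptom onset, age at severe RDS); two-tailed 0.05. The document states no sample size, power, event rate or margin, so there is no planned figure to reproduce. All group sizes, rates and correlations below are assumptions.

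**1. Question against method.**

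| What the question needs | What the Statistical Analysis section supplies |
|---|---|
| Biallelic versus no abnormality | Three-group test; no follow-up contrast |
| Single mutation versus no abnormality | Three-group test; no follow-up contrast |
| Size of any difference | p-value only |
| A basis for saying similar | None (no interval, no margin) |

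This gap does not depend on any assumed number.

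**2. How wide an interval might be.** Take the Newcombe 95% interval for a difference between two proportions, both observed near 50%. The Wilson half-width for one group of n is then (1.96/2)/√(n+1.96²), and the two combine in quadrature:

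half-width = 0.98 × √[1/(n₁+3.84) + 1/(n₂+3.84)]

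- 5 versus 30: 0.98 × √(1/8.84 + 1/33.84) = 0.370, or 37 points
- 10 versus 30: 0.98 × √(1/13.84 + 1/33.84) = 0.313, or 31 points
- 40 versus 40: 0.98 × √(2/43.84) = 0.209, or 21 points

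The simpler Wald formula gives 47, 36 and 22 points. It overstates the width in small groups, so the Newcombe values are the ones to use.

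**3. How often a real difference is missed.** Suppose the true rates are 60% in an ABCA3 group and 30% without an abnormality. Exact power of Fisher's test is 0.287 at 10 versus 30 and 0.725 at 40 versus 40. So p≥0.05 occurs in 1−0.287 = 71% and 1−0.725 = 27.5% of datasets.

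**4. Chance findings from the remedy.** Two unadjusted contrasts per outcome share the no-abnormality comparator. With assumed groups of 10, 10 and 30 and no true difference anywhere, simulation gives the share of datasets with at least one 95% interval excluding zero. The lower figure is for correlation 0.8 between outcomes, the upper for correlation 0:

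| Outcomes given contrasts | Share with at least one chance finding |
|---|---|
| 3 | about 18–26% |
| 8 (five more) | about 29–55% |
| 13 (ten more) | about 34–73% |

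**The case against.** **The groups are identified.** A reader might infer that the plan never says who is compared. It does: the aim and the sequencing section name the three groups, and ANOVA across three named groups is ordinarily a three-group test. This objection stands. Only the follow-up contrasts and the estimates are missing.

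**Nothing says p≥0.05 will be read as similarity.** A reader might infer that the plan intends this. No sentence states it, no equivalence hypothesis is set, and silence in a short statistical section does not show that estimates will go unreported. That also stands. But similarity is one of the two answers in the question the study says it addresses, and nothing in the plan could support it.

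**No main outcome, and a late document.** Admissions ended in December 2019 and the title block reads "Date of document: March 16, 2021". A reader might infer that no main outcome was ever chosen, or that the analysis was devised after the results were seen. The document shows neither. The study was registered and cites a 2018 approval number, and the registry record is not part of what was reviewed. What can be said is that this document names no main outcome and that results may already have been known.

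**The choice of contrasts is partly judgement.** The background words its question for ABCA3-mutated infants as one class, so a pooled contrast, or biallelic versus single, could be defended. The two proposed contrasts use the background's comparator and keep apart the classes for which it states separate expectations.

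**More contrasts mean more chance findings.** True, and an open-ended list of severity-related characteristics would make it worse. The remedy has to bound that list.

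**It is a retrospective cohort.** "This single-center retrospective cohort study involved infants": no allocation or treatment decision depends on these tests. That limits the consequence but leaves the interpretive gap.

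**Conclusion.** The point holds as a should-fix matter of analysis and reporting. As written, the plan provides no effect estimate, interval or follow-up contrast, so it can neither attribute a three-group difference to one ABCA3 group nor support a finding of similarity. Both statements rest on the text alone.

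The size is illustrative because no group sizes are given. Over the assumed range from 5 versus 30 to 40 versus 40, a zero observed difference in proportions near 50% would still be compatible with true differences of about 37 down to 21 points. Non-significance at such sizes is weak evidence of similarity. The documents do not support going further and saying that the groups are undefined, that the investigators will claim similarity from a non-significant test, or that the analysis is known to be post hoc.

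**What to change.** Keep the existing tests and add the following to the Statistical Analysis section.

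1. **Contrasts.** For the radiographic score, age at symptom onset and age at severe RDS, report biallelic versus no abnormality and single mutation versus no abnormality, each with an estimate and 95% confidence interval. Use a mean or median difference for the score. For the ages, use a difference in medians or a Hodges–Lehmann shift, with or without a hazard ratio. Every enrolled infant has severe RDS by the entry definition, so no censoring is expected and a shift in age can be estimated without assuming proportional hazards.
2. **Further characteristics.** Fix the list before group results are viewed. If results are already known, give both contrasts for every characteristic reported, not a chosen subset.
3. **Interpretation.** State that p≥0.05 is not read as similarity. Claim similarity only if the interval excludes a difference set before group results are seen; otherwise report the interval and make no such claim.
4. **Status.** Label the comparisons exploratory, because this document names no main outcome.

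**Cost.** A little more analysis of data already held, and some wording. Intervals will be wide if groups are small, and fewer firm statements will be possible. Multiplicity is the main downside: on the assumptions above, about 18–26% of null datasets would show at least one chance finding for the three outcomes, and more as characteristics are added. The fixed or complete list and the exploratory label make that risk visible but do not remove it.
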